2.1.4.3 Infusion associated reactions

IARs typically occur within 24 hours from the start of each isatuximab/REGN2810 infusion.

Whenever possible, a diagnosis of the IAR (eg, Cytokine release syndrome, infusion related reaction, anaphylactic reaction, or any other teams chosen by the investigator) will be reported by the investigator in a specific AE page. In addition, symptoms of the IARs will be reported on a separate eCRF form.

IARs will be analyzed based on the investigator reported term collected in the specific AE pages.

2.1.4.4 Deaths

The deaths will be summarized as follows:

- Deaths in TEAE period: includes all deaths occurring from the first IMP up to the end of treatment + 30 days
- Deaths in post-treatment period: includes all deaths occurring after the end of TEAE period up to study closure

2.1.4.5 Laboratory safety variables

Clinical laboratory data consists of blood and urine analysis including hematology, biochemistry and urinalysis. Clinical laboratory values will be converted into standard international units that will be used in all listings and tables.

Parameters measured on the day of the first study treatment infusion will be considered as part of the baseline measurements.

For laboratory safety variables, the treatment period is defined as the time from the first dose of study treatment (irrespective of treatment) administration to the last dose of study treatments + 30 days.

Blood and urine samples for clinical laboratories parameters will be taken as defined in the study flow charts and as clinically indicated. The laboratory parameters will be classified as follows:

- Hematology
 - **Hemoglobin and coagulation:** hemoglobin, hematocrit, red blood cell (RBC) platelet counts, prothrombin time or international normalized ratio (INR) and activated partial thromboplastin time (PTT)
 - **White blood cells (WBCs):** WBC count, leukocytes, neutrophils, lymphocytes, monocytes, basophils, eosinophils
- Biochemistry
 - **Metabolism:** fasting glucose, total protein
 - **Electrolytes:** sodium, potassium, chloride, calcium, albumin, magnesium, phosphate, bicarbonate/carbon dioxide

- **Renal function:** uric acid, serum creatinine, estimated creatinine clearance by modified diet in renal disease (MDRD) formula, urea or blood urea nitrogen (BUN)
- **Liver parameters:** alanine aminotransferase (ALT), aspartate aminotransferase (AST), alkaline phosphatase, total and direct bilirubin, lactate dehydrogenase (LDH)
- **Hormonal:** thyroid stimulating hormone (TSH) and free T4
- Urinalysis
 - Quantitative or semi-quantitative urinalysis: RBC, protein, glucose, pH, ketone, bilirubin, leukocytes, nitrates and specific gravity

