# 1.3 STUDY FLOWCHART FOR PHASE 1, PHASE 2 COHORTS A-1, A-2, B AND CROSS-OVER PART

	Screening/ Baseline	Cycle 1 b		1 b	Subsequent Cycles b	End of Treatment (EOT)	Post treatment safety follow-up period C		Survival follow-up C
Evaluation a	D-28 to D1	D1	D8	D15	D1	30 (±7) days after last IMP admin	At 60 (±7) days after last IMP admin	At 90 (±7) days after last IMP admin	Beyond 90 (±7) days after last IMP admin
Informed Consent / Inclusion/Exclusion Criteria	Х								
Demography, Medical/Surgical and Disease History d	Х								
Physical Examination 	X	Χ	Χ	Χ	Х	Х	Х	Χ	
Weight/Height (at baseline only) f	X	Χ	Χ	Χ	Х	Х			
Vital Signs g	X	Χ	Χ	Χ	X	Х	Х	X	
Performance Status (ECOG)	X	Х	Х	Χ	X	Х			
12-Lead ECG h	X				As clinically indicated				
Laboratory Assessments:									
Pregnancy Test i	X (within 7 days prior to first dose)	Х			X	Х	Х	x i	
Blood Chemistry j	X	χ k	Х	Χ	X	Х	Х	Х	
Hematology /	X	χ k	Χ	Χ	X	Х	Х	X	
Coagulation m	X				As clinically indicated				
Testosterone level	X								
Blood typing interference test n	X				Cycle 2 only				
Urinalysis 	X	x k			As clinically indicated	Х	Х	Χ	
PK p					See PK/pharmacody	ynamics Flow-Chart			
ADA q	See PK/pharmacodynamics Flow-Chart								
Exploratory biomarkers:									
Tumor biopsy for IHC analyses: CD38, PD-L1, immune contexture r	Х				X (Cycle 2 Day 1, unless clinically unfeasible and after discussion with Sanofi Medical Monitor)				

11-Jun-2019 Version number: 1

	Screening/ Baseline	(	Cycle	1 b	Subsequent Cycles b	End of Treatment (EOT)	Post treatment safety follow-up period C		Survival follow-up C
Evaluation a	D-28 to D1	D1	D8	D15	D1	30 (±7) days after last IMP admin	At 60 (±7) days after last IMP admin	At 90 (±7) days after last IMP admin	Beyond 90 (±7) days after last IMP admin
Tumor biopsy for transcriptomic analysis S	X				X (Cycle 2 Day 1, unless clinically unfeasible and after discussion with Sanofi Medical Monitor)				
Tumor biopsy for genomic characterization (tumor mutational load and MSI status) $^{t}$	х								
Blood sample for tumor mutational load control U	Х								
Blood sample for immune genetic markers V		Х							

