- g Vital Signs: Vital signs including blood pressure, heart rate, temperature, and respiration rate are required at Screening. The measurements will also be performed at the EOT visit, and post treatment follow up visits at 60 and 90 days after last treatment. For all patients, vital signs should be obtained prior to the start of each isatuximab infusion, 1 hour after the start of the infusion, at the end of infusion, and if clinically indicated during the infusion.
- h 12-Lead ECG: Single (not triplet). To be performed at Screening and then as clinically indicated.
- i Pregnancy Test: Women of child bearing potential must have a negative serum pregnancy test result within 7 days prior to first IMP administration. A pregnancy test (serum or urine) is to be done on Day 1 of each cycle prior to the study treatment, at the EOT visit, and every 30 (± 7) days until 6 months after the last dose of study treatment.
- **Blood Chemistry:** To be done at Screening, then prior to premedication and IMP administration, at the EOT visit, during follow-up and as clinically indicated. Biochemistry should be performed every 7 days in case of Grade 3/4 abnormalities. Blood chemistry includes: AST, ALT, bilirubin (total and direct), ALP, LDH, sodium, potassium, chloride, bicarbonate/carbon dioxide, calcium, magnesium, phosphate, uric acid, urea or BUN, serum creatinine, eGFR (MDRD formula; Appendix H), glucose (fasting), albumin and total protein. TSH will be assessed at baseline, every second cycle, EOT, during follow-up visits (60 and 90 days after last treatment); free T4 will be assessed if TSH is outside of the normal range.
- k Blood chemistry, hematology, PSA and urinalysis assessments are not required to be repeated prior to Cycle 1 Day 1 if the screening laboratory assessments were performed within 3 days prior to first IMP administration.
- Hematology: To be done at Screening, then prior to premedication and IMP administration, at the EOT visit, during follow-up and as clinically indicated. Hematology includes: Hemoglobin, hematocrit, RBC, WBC with differential, and platelet counts. If Grade 4 neutropenia, assess ANC every 2 to 3 days until ANC ≥0.5 × 10^9/L and at least weekly thereafter until ANC ≥1.0 × 10^9/L. Blood group card to be obtained before study entry.
- m Coagulation: To be done at Screening and then as clinically indicated. Coagulation includes: prothrombin time or INR and activated PTT.

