### 4.4.2.2 REGN2810

The safety profiles of the known anti-PD-1 agents are similar and most notably include a range of AEs considered as immune-related adverse events (irAEs) listed in the REGN2810 Investigator's Brochure. The most commonly observed treatment-related irAEs associated with these monoclonal antibodies are: fatigue, pyrexia, chills, infusion reactions, skin rash, diarrhea/colitis, endocrine toxicities, hepatic toxicities (mainly asymptomatic elevations in aspartate aminotransferase [AST] and alanine aminotransferase [ALT] levels), pneumonitis, uveitis, interstitial nephritis, pancreatitis and neurologic syndromes (52, 53). Increasing use and an understanding of how to manage the adverse reactions associated with these agents appears to be have lessened the morbidity as well as the mortality associated with severe irAEs (53).

Cumulatively, as of 20 January 2017, 459 patients have been treated with REGN2810 either as monotherapy or in combination with radiotherapy and/or other cancer therapy in the 3 ongoing studies. Below are summary from the 2 studies in solid tumors (REGN2810 is being evaluated in two Phase 1 clinical studies: R2810-ONC-1423 and R1979 ONC-1504), and one Phase 2 clinical study: R2810-ONC-1540.

R2810-ONC-1423 is a first-in-human repeat dose study with REGN2810 as single therapy and in combination with other anti-cancer therapies in patients with advanced malignancies. As of 20 January 2017, a total of 353 patients have been enrolled and treated with different dose levels

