#### 10.5 OBLIGATION OF THE INVESTIGATOR REGARDING SAFETY REPORTING

#### 10.5.1 Adverse events

All AEs regardless of seriousness or relationship to the IMP, spanning from the signature of the informed consent form (ie, occurring during the baseline period even in the absence of any administration of IMP), up to 30 days following the last administration of study treatment, are to be recorded on the corresponding page(s) included in the e-CRF.

Whenever possible, a diagnosis or single syndrome should be reported instead if symptoms. The Investigator should specify the date of onset, intensity, action taken with respect to IMP, corrective treatment/therapy given, additional investigations performed, outcome, and his/her opinion as to whether there is a reasonable possibility that the AE was caused by the IMP.

Vital signs or ECG abnormalities are to be recorded as AEs only if they are symptomatic and/or requiring corrective treatment and/or lead to treatment discontinuation and/or modification of dosing and/or fulfill a seriousness criterion and/or are defined as AESIs (see Section 10.5.5).

Laboratory abnormalities are to be recorded as AEs only if they lead to treatment discontinuation and/or modification of dosing and/or fulfill a seriousness criterion and/or are defined as AESIs (see Section 10.5.5).

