#### 13.4.5.4 Clinical laboratory evaluations

Clinical laboratory values will be analyzed after conversion into standard international units. International units will be used in all listings and tables. Complete blood count and serum chemistry results will be graded according to NCI-CTCAE version 4.03, when applicable. For patients with multiple occurrences of the same laboratory variable during the TEAE period, the maximum grade (worst) per patient will be used. The denominator used for percentage calculation is the number of patients with at least 1 evaluation of the laboratory test during the considered observation period.

The number and proportion of patients with abnormal laboratory tests at baseline (ie, last assessment before the first dose of study treatments administration) will be presented for all grades together and each grade separately. Similar tables showing abnormalities during the TEAE period will be provided.

When the NCI-CTCAE version 4.03 scale is not applicable, the number of patients with a laboratory abnormality out-of-normal laboratory range value will be displayed.

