2.4.6.4 Analyses of laboratory variables

Each laboratory test result will be graded by CTCAE criteria (version 4.03), when applicable. For hematological parameters and for some biochemistry parameters, Sanofi sponsor generic normal ranges will be used for the grading of laboratory abnormalities (see list of parameters in [Table 6](#) and [Table 7](#)). For other biochemistry parameters (eg, for hepatic parameters), grading will be derived using the local laboratory normal ranges.

The number (%) of patients with abnormal laboratory tests at baseline and during the on-treatment period will be presented by all grades and each grade. For patients with multiple occurrences of the same laboratory variable during the on-treatment period, the maximum grade (worst) per patient will be used.

The denominator used for percentage calculation is the number of patients with at least 1 evaluation of the laboratory test during the considered observation period.

When appropriate, the summary table will present the frequency of patients with any grade of abnormal laboratory tests and with Grade 3-4 abnormal laboratory tests.

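### Laboratory results from days 60 and 90, and end-of-treatment samples drawn after day 30, enter no planned laboratory table

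*SAP*

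**What the plan says.** **Collection.** The flowchart in protocol 1.3 schedules chemistry and haematology at the end-of-treatment (EOT) visit, timed at "30 (±7) days after last IMP admin", and at days 60 and 90, each with the same 7-day tolerance. Protocol 12.4 and 12.5.1 list the panels, which include AST, ALT, bilirubin, creatinine and TSH. The chemistry footnote to the flowchart reads "TSH will be assessed at baseline, every second cycle, EOT, during follow-up visits (60 and 90 days after last treatment").

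**Analysis.** SAP 2.1.4.5 defines the laboratory treatment period as running from "first dose of study treatment (irrespective of treatment) administration to the last dose of study treatments + 30 days". SAP 2.4.6.4 then states that patients with "abnormal laboratory tests at baseline and during the on-treatment period will be presented by all grades and each grade". No other laboratory table is planned. Protocol 13.4.5.4 likewise confines its tables to baseline and the treatment-emergent (TEAE) period, which also ends 30 days after the last dose.

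**Adverse event rule.** Protocol 10.5.1: "Laboratory abnormalities are to be recorded as AEs only if they lead to treatment discontinuation and/or modification of dosing", or if they are serious or count as an adverse event of special interest (AESI).

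**Ungraded tests.** Protocol 13.4.5.4: "When the NCI-CTCAE version 4.03 scale is not applicable, the number of patients with a laboratory abnormality out-of-normal laboratory range value will be displayed". SAP 2.4.6.4 has no counterpart, and SAP 1.5 declares no modification to the protocol's statistical section.

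**The concern.** Patients attend two safety visits whose laboratory results no planned laboratory summary uses, and a late EOT sample is lost in the same way. SAP 2.1.4 defines a post-treatment period and the SAP uses it for adverse events and deaths, but not for laboratory data, so this reads more like an omission than a reasoned choice.

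Adverse event reporting covers only part of the gap. Protocol 4.4.2.2 describes one of the known harms of the anti-PD-1 class as "hepatic toxicities (mainly asymptomatic elevations in aspartate aminotransferase [AST] and alanine aminotransferase [ALT] levels"). A finding of that kind, seen first at day 60 or 90 and not serious, is what the reporting rule is least likely to turn into an adverse event once dosing has stopped. Safety is the primary objective of Phase 1 and a secondary objective of Phase 2, so the safety tables should use the safety data that are collected.

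**Working it through.** The plan states no figure for this point, so there is none to reproduce. The check compares visit windows with the cut-off, then follows a late laboratory finding through the reporting rules.

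**1. Windows against the cut-off.** Inputs: visits at 30, 60 and 90 days, each ± 7 (protocol 1.3); cut-off at last dose + 30 days (SAP 2.1.4.5). Counting whole days:

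| Visit | Permitted days | Inside (day 30 or earlier) | Outside |
|---|---|---|---|
| EOT | 23 to 37 (15 days) | 8 | 7 |
| Day 60 | 53 to 67 (15 days) | 0 | 15 |
| Day 90 | 83 to 97 (15 days) | 0 | 15 |

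At most one of the three post-dose visits can count. If EOT visits were spread evenly over the window, 7/15 = 47% of EOT samples would be lost. That is an illustration only. Protocol 12.4 brings the EOT visit forward when another anticancer therapy starts, which lowers the share.

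**2. No rule rescues the late EOT sample.** The only laboratory windowing rule, SAP 2.5.4, assigns tests to treatment cycles by date. It does not mention the EOT, day-60 or day-90 visits.

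**3. Routes from a late laboratory finding to an adverse event.** Protocol 10.5.1 gives four:

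- Treatment discontinuation: closed, because dosing has ended.
- Dose modification: closed for the same reason.
- Seriousness: open.
- AESI: the general immune-related item covers TEAEs (protocol 10.5.5, SAP 2.1.4.2), so it ends at day 30. The item for patients with a prior PI3K inhibitor who receive REGN2810 has no such limit and stays open. The other items (dose-limiting toxicity, infusion reaction, pregnancy, overdose) do not fit a late laboratory finding.

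Apart from these, an investigator may report a diagnosis, which protocol 10.5.1 prefers to symptoms. A non-serious abnormality with no diagnosis, in a patient without a prior PI3K inhibitor, has no route.

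**4. Possible size.** The documents give no rate of abnormalities that first appear after day 30. Assuming 2% to 10% of patients, and full follow-up of a completed cohort:

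- mCRPC, n = 49: 49 × 0.02 = 1.0 to 49 × 0.10 = 4.9 patients.
- NSCLC, n = 36: 36 × 0.02 = 0.7 to 36 × 0.10 = 3.6 patients.

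These would be missing from the laboratory tables. Some would still appear as adverse events through the routes in step 3.

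**The case against.** The strongest reply is that the 30-day cut is a consistent convention. It matches the TEAE period and implements protocol 13.4.5.4, so the SAP does not depart from the protocol here. That stands: the point is an improvement to both documents, not an SAP deviation. It does not explain why laboratory data alone, among adverse events, deaths and laboratory results, have no post-treatment summary.

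Other safeguards exist. New related events after day 30 are followed (protocol 9.1.2 and 12.5.1). SAP 2.4.6.2 plans a post-treatment adverse event table by organ class and preferred term, for all grades and for Grade 3 or higher. Listings are mentioned without a period, and the data monitoring committee reviews ongoing safety data at least every three months (protocol 6.9).

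A reader might therefore infer too much from the gap:

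- *That late liver and thyroid toxicity goes unreported.* It does not follow. Serious or related events and diagnoses such as hepatitis or hypothyroidism reach the adverse event table.
- *That the late samples are there to detect immune toxicity.* The stated purpose is anti-drug antibody and general safety assessment.
- *That these harms show only in laboratory data.* Protocol 4.4.2.2 says mainly asymptomatic of the AST/ALT rises, not of endocrine events, which Appendix G describes with symptoms.
- *That drug persistence measures the loss.* The 28-day half-life is isatuximab's. The harms cited belong to the anti-PD-1 class, and no REGN2810 half-life is given.
- *That a fixed share of each patient's TSH values is lost.* The flowchart says every second cycle, but protocol 12.3.1 lists TSH in the Cycle 1 chemistry panel, so the denominator is not settled.
- *That early stoppers, and so the patients with most toxicity, lose most.* The documents give no reasons-for-stopping figures.

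On ungraded tests, SAP silence might mean that the protocol rule still applies. It may, but the table is then unspecified. The documents do not show which tests CTCAE 4.03 leaves ungraded, so whether TSH and free T4 are affected is open.

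**Conclusion.** The point holds in a limited form. As written, every day-60 and day-90 laboratory result, and any EOT sample from days 31 to 37, is collected but summarised in no laboratory table. A non-serious, purely laboratory abnormality first seen then would generally appear in no table at all, except through the AESI for patients with a prior PI3K inhibitor.

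The window result needs no assumption beyond reading the SAP's on-treatment period in 2.4.6.4 as the period defined in 2.1.4.5. The 47% share assumes evenly spread visits, and the patient counts rest on an assumed 2% to 10% rate. Patients still on treatment after the study cut-off have little follow-up data collected (protocol 12.5.3), so not everyone contributes three post-dose panels.

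The missing out-of-range display is a separate, smaller inconsistency between SAP 2.4.6.4 and protocol 13.4.5.4. Neither part affects the response-rate analysis. The change should be made because it is cheap and uses safety data that patients have already provided.

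**What to change.** In SAP 2.1.4.5 and 2.4.6.4:

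1. Assign the scheduled EOT sample to the on-treatment period by visit, whatever its day within the ± 7 window.
2. Add a post-treatment table, through the day-90 visit plus 7 days (day 97), of worst CTCAE grade with shift from baseline, at minimum for AST, ALT, bilirubin and creatinine. Flag results obtained after the start of new anticancer therapy.
3. Restore the protocol's out-of-range display for any test without a CTCAE grade, on treatment and to day 90, after checking whether this covers TSH and free T4.

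Record the wider period in SAP 1.5, since protocol 13.4.5.4 stops at the TEAE period. The cost is SAP wording and a few extra tables. No visit, sample or clinical rule changes. The drawback is that some late abnormalities will reflect progression or subsequent therapy. The flag handles the second. The first needs a caution when the table is read.

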2.1.4.6 Vital signs variables

Vital signs include: heart rate, systolic and diastolic blood pressure, respiratory rate, weight and temperature.

For vital signs, each assessment performed at cycle 1 Day 1, Day 8 and Day 15 prior to study treatment administration unless specified otherwise and at cycle N, Day 1.

Thus, parameters measured on the day of the first study treatment infusion will be considered as part of the baseline measurements.

For vital signs, the treatment period will start at first study treatment infusion + 1 day.

For a given parameter, a patient (respectively a cycle) will be considered as evaluable if at least one measure of this parameter is available during the on-treatment period.

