## 13.4.5.2 Analyses of adverse events

The observation period will be divided into 3 segments: pretreatment, TEAE and posttreatment:

- The pretreatment period is defined as the time informed consent is signed until the first dose of study treatments administration.
- The TEAE period is defined as the time from the first dose of study treatments up to 30 days after last dose of study treatments.

11-Jun-2019 Version number: 1

• The posttreatment period is defined as the time starting 31 days after the last dose of study treatments to study closure or death, whichever comes first.

Pretreatment AEs are defined as any AE during the pretreatment period.

Treatment-emergent AEs are defined as AEs that develop, worsen (according to the Investigator opinion) or become serious during the TEAE period.

Posttreatment AEs are defined as AEs that are reported during the posttreatment period.

The grade will be taken into account in the summary. For patients with multiple occurrences of the same PT, the maximum grade will be used.

The primary focus of AE reporting will be on TEAEs. Pretreatment and posttreatment AEs will be described separately.

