## 13.4.5.5 Vital signs

Potentially clinically significant abnormality (PCSA) values are defined as abnormal values considered medically important by the Sponsor according to predefined criteria/thresholds based on literature review. The incidence of PCSA during the TEAE period will be summarized.

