1.5 MODIFICATIONS TO THE STATISTICAL SECTION OF THE PROTOCOL

Not applicable.

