2.1.4 Safety endpoints

The safety analysis will be based on the reported adverse events (AEs) and other safety information, such as clinical laboratory data, vital signs, weight, electrocardiogram (ECG) and Eastern Cooperative Oncology Group (ECOG) performance status.

Observation period

The observation period starts from the time when the patient gives informed consent and is divided into 3 periods:

- **The pre-treatment period** is defined as the time informed consent is signed until the first dose of study treatments administration

- The **treatment-emergent adverse event (TEAE) period** is defined as the time from the first dose of study treatments up to 30 days after last dose of study treatments
- The **post-treatment** period is defined as the time starting from 31 days after the last dose of study treatments to the end of the study (as defined in the protocol)

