2.4.6.5 Analyses of vital sign variables

The incidence of vital signs potentially clinically significant abnormality (PCSA) ([Table 4](#)) any time during the on-treatment period will be summarized by treatment group irrespective of the baseline level and/or according to the following baseline status categories:

- Normal/missing
- Abnormal according to PCSA criterion or criteria

Table 4 - Potentially clinically significant abnormalities criteria for vital signs

Parameter	PCSA
HR	≤50 bpm and decrease from baseline ≥20 bpm ≥120 bpm and increase from baseline ≥20 bpm
SBP	≤95 mmHg and decrease from baseline ≥20 mmHg ≥160 mmHg and increase from baseline ≥20 mmHg
DBP	≤45 mmHg and decrease from baseline ≥10 mmHg ≥110 mmHg and increase from baseline ≥10 mmHg
Weight	≥5% increase from baseline ≥5% decrease from baseline

Temperature and respiratory rate will be summarized at baseline and end of treatment. A listing of patients with at least one PCSA will be provided.

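### The SAP opens the vital-sign treatment period one day after the first infusion, so heart-rate and blood-pressure readings taken during and at the end of that infusion drop out of the PCSA table, with no declared change from the protocol

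*SAP*

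**What the plan says.** SAP 2.1.4.6 sets the window: "For vital signs, the treatment period will start at first study treatment infusion + 1 day". The same section places values from the day of the first infusion with baseline. SAP 2.4.6.5 tabulates PCSA incidence "any time during the on-treatment period will be summarized by treatment group". PCSA thresholds are given for heart rate, systolic and diastolic blood pressure, and weight. The other two parameters have none: "Temperature and respiratory rate will be summarized at baseline and end of treatment".

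The protocol uses a different window. Section 13.4.5.5 says: "The incidence of PCSA during the TEAE period will be summarized". Section 13.4.5.2 fixes where that period begins: "The TEAE period is defined as the time from the first dose of study treatments". SAP 2.1.4 gives the same definition for its own TEAE period, which "is defined as the time from the first dose of study treatments up to 30 days after last dose of study treatments".

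For the measurement schedule, footnote g of the flowchart in Protocol 1.3 requires vital signs "prior to the start of each isatuximab infusion, 1 hour after the start of the infusion, at the end of infusion", and Protocol 4.4.4 repeats this. Protocol 12.3.1 asks for hourly readings during the infusion plus one at its end.

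SAP Section 1.5, headed "MODIFICATIONS TO THE STATISTICAL SECTION OF THE PROTOCOL", records that none applies.

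**The concern.** The protocol requires these readings and says they should count, yet the SAP closes the window to them. Protocol 4.4.2.1 says infusion reactions are most common at the first isatuximab administration and tend not to recur later, so the day left out is the one on which an infusion-related change in heart rate or blood pressure is most likely. Later infusions are an imperfect substitute. For example, Protocol 6.6.5 has a patient stop both drugs after a Grade 3 or higher reaction that begins once isatuximab has started. If that happens at the first infusion, there is no later infusion at which a crossing could be counted.

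What is at stake is a descriptive safety table. It would understate the incidence, and a reader relying on the protocol's definition would not know that the first infusion is missing.

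**Working it through.** **1. The two windows side by side**

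| Source | Start of the period used for PCSAs |
|---|---|
| Protocol 13.4.5.5 with 13.4.5.2 | first dose |
| SAP 2.1.4 (general TEAE period) | first dose |
| SAP 2.1.4.5 (laboratory) | first dose |
| SAP 2.1.4.6 (vital signs) | first infusion + 1 day |

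Only vital signs are shifted. The laboratory section also places first-day values with baseline, yet keeps a first-dose start.

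**2. Do the first-infusion readings fall before + 1 day?**

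Inputs: dose 10 mg/kg (Protocol 8.1.1.2); first-infusion rate 175 mg/h for 1 h, then 50 mg/h more every 30 min up to 400 mg/h (Protocol 8.3.1.1). Body weights are assumed.

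Cumulative dose: 175 mg at 1 h; 175 + 0.5 × 225 = 287.5 mg at 1.5 h; + 0.5 × 275 = 425 mg at 2 h; + 0.5 × 325 = 587.5 mg at 2.5 h; + 0.5 × 375 = 775 mg at 3 h; then 400 mg/h.

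Duration = time at the last completed step + remaining dose ÷ current rate. At 50 kg: 2 + (500 − 425)/325 = 2.23 h. At 80 kg: 3 + (800 − 775)/400 = 3.06 h.

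| Weight (kg) | Duration (h) | Flowchart readings after start | Hourly + end (12.3.1) |
|---|---|---|---|
| 50 | 2.23 | 2 | 3 |
| 60 | 2.53 | 2 | 3 |
| 70 | 2.80 | 2 | 3 |
| 80 | 3.06 | 2 | 4 |
| 90 | 3.31 | 2 | 4 |
| 100 | 3.56 | 2 | 4 |
| 110 | 3.81 | 2 | 4 |
| 120 | 4.06 | 2 | 5 |

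These durations agree with the 2 to 4 hours in Protocol 8.3.1. In the combination cohorts REGN2810 adds 30 minutes beforehand: 4.06 + 0.5 = 4.56 h at 120 kg, ignoring any gap between the infusions. An interrupted isatuximab dose is to be finished the same day (Protocol 6.6.5, Table 4). Every scheduled reading of the first infusion therefore precedes the window.

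**3. Does another rule bring them back?**

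SAP 2.5.5 lets unscheduled measurements feed worst on-treatment values. It covers neither scheduled readings nor the start of the period.

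**4. Size per missed patient**

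1/49 = 2.04 percentage points (full mCRPC cohort); 1/36 = 2.78 points (full NSCLC cohort). If a cohort stops after Stage 1: 1/23 = 4.35 and 1/20 = 5.00 points.

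The documents give no rate of such crossings. As an assumption only, if 1% to 10% of patients had their sole, otherwise unreported crossing at the first infusion, the table would miss 49 × 0.01 = 0.49 to 49 × 0.10 = 4.9 patients of 49, or 36 × 0.01 = 0.36 to 36 × 0.10 = 3.6 of 36.

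**The case against.** **Pre-dose readings only.** SAP 2.1.4.6 introduces vital signs as assessments made before dosing unless specified otherwise. One could infer that only pre-dose values are analysed at any visit, in which case the + 1 day rule merely keeps the Day 1 pre-dose value out and deleting it restores nothing. This does not hold. The wording mirrors Protocol 12.3.1, which does specify otherwise for vital signs by scheduling readings during and at the end of the infusion.

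**Terminology.** The + 1 day sentence says treatment period, while SAP 2.4.6.5 says on-treatment period, a term SAP 2.4.6.3 uses for deaths in the TEAE period. But SAP 2.1.4.6 uses both terms in adjacent sentences, and the SAP defines no other window for vital signs.

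**Delegation.** Protocol Section 13 leaves detailed specifications to the SAP. Moving the start of a period that the protocol has defined goes beyond added detail, and SAP 1.5 exists to record such a change.

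**Importance.** This objection largely stands and limits the point. Protocol 10.5.1 makes a vital-sign abnormality an adverse event if it is symptomatic, treated, changes dosing, stops treatment, is serious or is of special interest. Infusion reactions, including those at the first infusion, have their own outputs in SAP 2.4.6.2. The patients lost altogether are those whose crossing met none of these criteria.

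**Unseen eCRF.** This also stands. The documents do not show whether in-infusion readings are captured with a time-point, and the assumed 1% to 10% range has no anchor in them.

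**Conclusion.** The concern holds. As written, the SAP excludes every scheduled heart-rate and blood-pressure reading taken during and at the end of the first infusion from the PCSA incidence. That conflicts with the protocol's window and with the SAP's own TEAE definition, and no change is declared. The exclusion covers at least 2 scheduled readings per patient; the 3 to 5 under the hourly schedule rests on the assumed weights.

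The consequence is limited. Temperature and respiratory rate have no PCSA threshold, and weight is not measured during an infusion. Incidence is per patient, so someone who crosses at a later infusion still counts. Adverse-event, infusion-reaction and special-interest outputs are unaffected. A patient disappears from all summaries only if the sole crossing is at the first infusion and is not reported as an adverse event or infusion reaction. How many there would be cannot be derived. The percentage-point effects assume that all 49 or 36 patients are evaluable. No primary conclusion changes, but the rule should be corrected before the table is produced.

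The Day 1 baseline sentence is not itself a contradiction, because SAP 2.1.1 allows exceptions to its baseline definition. It does need clearer wording: read literally, a value taken during or after the infusion could become the reference for the change-from-baseline part of the PCSA criteria.

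**What to change.** First check that the eCRF records a time-point label or clock time for Day 1 vital signs. Without one, moving the window would count pre-dose Day 1 values as on-treatment.

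If it does, revise two sentences of SAP 2.1.4.6:

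- Replace the + 1 day rule with a start at the first dose of study treatment, matching Protocol 13.4.5.2 and 13.4.5.5 and SAP 2.1.4.
- Define vital-sign baseline as the last reading before that dose, and classify Day 1 readings taken during or after infusion as on-treatment, using the scheduled time-point or recorded time.

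If the later start is intended, state and justify it in SAP 1.5 and add a footnote to the PCSA table saying that first-infusion readings are excluded.

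The cost is the eCRF check, two sentences of SAP text and the matching derivation. No visits or assessments are added.
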